**Survey C1**

Please tell us how much you agree with the following statements:

1. *I am satisfied with the overall look of how the information was presented.*

I do not agree at										I fully agree
all										
1	2	3	4	5	6	7	8	9	10	

2. *I would understand the text better if there was more information about ECV procedure when turning babies.\**

I do not agree at all  
 1 2 3 4 5 6 7 8 9 10 I fully agree

3. *I wish this information was presented with more pictures or graphs.\**

I do not agree at all  
 1 2 3 4 5 6 7 8 9 10 I fully agree

4. *This information was hard to follow.\**

I do not agree at all  
 1 2 3 4 5 6 7 8 9 10 I fully agree

5. *I think this way of information presentation is easily memorized.*

I do not agree at all  
 1 2 3 4 5 6 7 8 9 10 I fully agree

\*Reverse scored item.

C.2. Accessibility of relevant information: This section of the survey will have 5 questions concerning how easy it was for the participant to find relevant information, measured by a 10-point Likert type scale where the answer 1 means *I do not agree at all* and 10 means *I fully agree*. The total score is the sum of scores on all the answers (maximum 50). The items for measuring accessibility of information will be:

**Survey C2**

1. *It was easy to recall the information about EVC procedure needed to answer the test questions.*

I do not agree at all  
 1 2 3 4 5 6 7 8 9 10 I fully agree

2. *I think this information is understandable to someone who does not have an experience with the topic.*

I do not agree at all  
1 2 3 4 5 6 7 8 9 10 I fully agree

3. *This topic is not possible to grasp with this small amount of information.\**

I do not agree at all  
1 2 3 4 5 6 7 8 9 10 I fully agree

4. *I think I need more information in order to decide about the benefits of ECV procedure.\**

I do not agree at all  
1 2 3 4 5 6 7 8 9 10 I fully agree

5. *I think I could explain to someone the benefits of ECV procedure using the information from this text only.*

I do not agree at all  
1 2 3 4 5 6 7 8 9 10 I fully agree

*\*Reverse scored item*

C3. Health numeracy: This section will use 6-item General health numeracy test (Osborne et al., 2013) in order to determine how much our participants understand the basic health instructions regarding numeracy dimension. For each correct answer, the participants receive one point and the total score is the sum of all correct answers.

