### Interventions

Infographics format of a Cochrane systematic review summary represents the experimental intervention in the trial. The control groups will receive either PLS (which represent text format with simple explanation of the survey topic main findings and is intended for lay audience) or the scientific summary (the text written for the academic population and practitioners) groups. We will use formats already available for the systematic review on external cephalic version for breech presentation before term (Hutton et al, 2015.).

All three types of Cochrane summaries will be translated into Croatian by the trial organizers, and back translated to English by an independent language expert to ensure the quality of the Croatian translation. The survey instrument will be in Croatian.

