### Outcomes

The results for each participant will be the sum of correct answers at the knowledge test as the primary outcome, while secondary outcomes will be the number of correct answers on health numeracy and the scores on Likert-type scales for accessibility and satisfaction.

a) Demographic characteristics

Participants will first provide information about their gender, age, knowledge about or prior experiences with Cochrane reviews and Cochrane Library, obtained specialization or PhD.

b) Primary outcome: Understanding the information from the review summary

The primary outcome of the study is the score on a knowledge test with ten questions about information contained in all three forms of presentation. The questions will focus on understanding the benefits and risks of the intervention and the quality of evidence described in the systematic review.

Each correctly answered question will be awarded one point, with a maximum of 10 points. Prior research on PLSs (Vandvik et al., 2012) used multiple choice questions with a single correct answer to assess understanding of PLS. However, multiple choice questions are closed questions and the correct answer may provide a visual reminder to the participant and thus do not measure real understanding of the material (Choi & Pak, 2005). In order to reduce this measurement bias, we will use open questions to assess knowledge of the participants.

c) Secondary outcomes

C.1. Reading experience: This section of the survey will include 5 questions about the experience of participants about the text they read, measured on a 10-point Likert type scale, where 1 means *do not agree at all* and 10 means *fully agree*. The total score is the sum of scores on all five answers (maximum 50).

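### Rating items in Surveys C1 and C2 can mean different things in each arm: one asserts that the information is small, two call it a text, and four score its amount or pictures

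*Combined protocol and SAP*

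**What the plan says.** Reading experience (Outcomes, C.1) and accessibility of information (C.2, introduced at the end of the Survey C1 section) are each the sum of five items rated 1 to 10, with a maximum of 50. C.2 is introduced as a measure of how easily the participant located the relevant information. A footnote to each survey marks the asterisked items as "Reverse scored item": items 2, 3 and 4 in C1, and items 3 and 4 in C2.

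The items at issue are:

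- C1 item 2, reversed: "I would understand the text better if there was more information about ECV procedure when turning babies".
- C1 item 3, reversed: "I wish this information was presented with more pictures or graphs".
- C2 item 3, reversed: "This topic is not possible to grasp with this small amount of information".
- C2 item 4, reversed: "I think I need more information in order to decide about the benefits of ECV procedure".
- C2 item 5, scored directly, which asks whether the respondent could explain the benefits "using the information from this text only".

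The same items go to all arms. Trial design describes the formats as a visual in plain language, plain language, and scientific language. Interventions describes the plain language summary as a format "which represent text format with simple explanation of the survey topic main findings" and the scientific summary as written for academics and practitioners. Ready-made formats are used, and no length is given for any of them.

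The section on claiming non-inferiority assigns superiority tests to the secondary outcomes and expects them to favour the infographic on satisfaction and accessibility. Inferential statistics (Table 1) compares the totals by Kruskal-Wallis or ANOVA. The only stated check of the instrument is expert review of face validity (Trial design).

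**The concern.** A comparison of totals between arms assumes that respondents in each arm answer the same question. Three features put that in doubt.

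1. C2 item 3 builds in its own premise. A respondent who thinks the amount was not small has no clear way to answer, and the number of such respondents may differ by arm.
2. Some items score a property of the format instead of the stated construct. A participant who found everything easily but wanted more detail loses points on accessibility. A participant who wanted pictures loses points on reading experience, and only one arm is a visual presentation.
3. C1 item 2 and C2 item 5 call the material a text, which does not describe the infographic.

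At stake is the interpretation of the two superiority claims. A difference between arms, or its absence, could partly reflect how the items fit each format. The plan has no item-level analysis that would reveal this, and face validity review does not test whether items work alike across formats.

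**Working it through.** **Scale arithmetic.** Five items at 10 points give 5 × 10 = 50, which reproduces the stated maximum. The minimum is 5 × 1 = 5, so the usable range is 50 − 5 = 45 and each item spans 10 − 1 = 9.

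| Items | Feature scored | Share of the range |
|---|---|---|
| C1 items 2 and 3 | wanting more information; wanting more pictures or graphs | 2 × 9 = 18 of 45 (40%) |
| C2 items 3 and 4 | whether the amount was enough | 2 × 9 = 18 of 45 (40%) |

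**Construct against item.** C2 is defined by ease of finding information. Items 3 and 4 concern sufficiency for grasping the topic or for deciding, which is a different question. C1 is defined more loosely, as the participant's experience of what was read, so a wish for more information or pictures can belong there. Its answer still depends on what the format contains.

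**Direction.** For an artefact that depends on length, the format lengths would be needed, and they are not given. The tilts may also oppose each other. C1 item 3 plausibly favours the infographic, which already consists of visuals. C1 item 2 and C2 items 3 and 4 would count against whichever format readers find too brief. C1 item 3 cannot offset anything in C2, because the totals are separate.

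**Size, as illustration only.** Let δ be a shift in the total between two arms that comes only from item wording or format features, with no true difference in the intended construct. By the normal approximation, the chance of a two-sided p<0.05 in the direction of the shift is

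Φ( δ / (σ√(2/n)) − 1.96 ).

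Inputs: n = 15 per arm (the minimum in Sample size); α = 0.05 (same section; sidedness not stated, two-sided assumed); σ, the SD of the total, assumed to be 6 to 10 because none is documented. √(2/15) = 0.365.

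| Shift in the total | σ = 6 | σ = 8 | σ = 10 |
|---|---|---|---|
| 4 points (2 on each of two items) | 45% | 28% | 19% |
| 2 points (1 on each of two items, or 2 on one) | 15% | 10% | 8% |

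Example: δ = 4 and σ = 8 give 4/(8 × 0.365) = 1.37, and Φ(1.37 − 1.96) = Φ(−0.59) = 28%. With no artefact, the figure in a given direction would be 2.5%.

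This is a two-arm approximation, whereas the plan names a three-group test. A larger sample would not remove the problem: in the formula a fixed shift becomes easier to detect as n grows.

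**The case against.** The strongest reply is that the intervention is the ready-made format as a whole, including how much it conveys. If readers of one format feel they need more, that is a real effect of the format. This stands to a fair degree for C1, whose definition is broad. It is weaker for C2, whose definition is specific, and it does not rescue C2 item 3, where the fault is an asserted premise.

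All three formats are summaries of one review, so respondents in every arm might read *small* relative to the full review. That is possible, but the item does not say so. The survey will be in Croatian, so the English words are not those that respondents see, and Outcomes itself uses *text* for all arms. This weakens the complaint about *text*, which is the least serious part, and is a reason to check the Croatian version too.

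Three stronger readings are tempting and are not supported:

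- *Several items presuppose a short text.* Only C2 item 3 does. The wording of C2 item 5 presupposes a medium, implies nothing about length, and is not reverse scored.
- *Both totals are pushed against the infographic and towards the scientific summary.* That requires the infographic to be the shortest format, which the documents do not say, and it overlooks C1 item 3, which plausibly works the other way.
- *The loss of power or the false-positive rate can be stated.* Any such figure rests wholly on assumed shifts and SDs.

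Dropping the affected items from the main totals has its own costs. Without C2 items 3 and 4, only the directly scored items 1, 2 and 5 remain, so control of acquiescence is lost. Removing C1 item 2 but keeping item 3 would leave C1 tilted by item 3.

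**Conclusion.** The point holds as a risk of non-equivalent measurement between arms. It can be read from the instrument: one loaded item (C2 item 3), two C2 items outside the stated construct, two C1 items that score features of the format, and two references to a text that do not fit the infographic. The format-dependent items make up 40% of the range of each total.

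Neither the direction nor the size of any resulting bias can be derived. The illustrative range, about 8% to 45% of trials significant with no true difference in the intended construct, depends on assumed shifts of 2 to 4 points and an assumed SD of 6 to 10. It shows sensitivity and predicts nothing.

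The primary knowledge score is unaffected. The point still merits action, because the superiority claims on satisfaction and accessibility rest on these two totals and the remedy costs almost nothing before launch.

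**What to change.** Before launch, in the Croatian version as well as the English:

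1. Reword C2 item 3 neutrally, for example *The amount of information given was enough to grasp the topic*, and score it directly.
2. Replace *text* by *summary* in C1 item 2 and C2 item 5.

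In the analysis plan:

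3. Keep the five-item totals as the main secondary outcomes.
4. Prespecify reporting of each item by arm.
5. Prespecify a sensitivity total that leaves out C1 items 2 and 3 and C2 items 3 and 4. Each scale then has three items (range 3 to 30). If a superiority conclusion differs between the main and sensitivity totals, say so when reporting it.

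If the wording can no longer be changed, steps 3 to 5 still apply, and C2 item 5 should be left out of the sensitivity total as well.

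The cost is three wording changes, a small amount of extra analysis, and one fewer reverse-scored item in C2 (item 4 alone would remain). The three-item totals will be somewhat less reliable, which is why they serve as a sensitivity analysis and not as replacements.

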### Survey C3

1. Call your physician if you have a temperature of 38°C or higher. The thermometer shows the following temperature:

37.9°C

Will you call your physician?

ANSWER: YES NO

2. If 4 out of 20 persons are at risk of getting a cold, what would the risk of getting a cold be?

ANSWER: \_\_\_\_\_.%

3. Let us assume that a 60-year-old woman has a maximum heartrate of 160 heartbeats per minute and that she was told to exercise until she reaches 80% of her maximum heartrate. How many heartbeats per minute is equal to 80% of her maximum heartrate?

ANSWER: \_\_\_\_\_heartbeats per minute

4. You have eaten half a bowl of carrots. How many grams of carbohydrates have you eaten?

---

**Food information**

Serving: 1 portion (85 g)

Portions per bowl: 2.5

---

**Amount per portion**

**Calories** 45

Calories from fat 0

---

Daily amount %

**Fats** 0g

0%

Saturated fats 0g

0%

**Cholesterol** 0g

0%

**Sodium** 55g

2%

**Total carbohydrates** 10g

3%

Dietary fiber 3g

12%

Sugars 5g

**Protein** 1g

---

ANSWER: \_\_\_\_\_grams

5. Your physician has informed you that your cholesterol is high. He explains to you that you have a 10% chance (risk) of having a heart attack in the next 5 years. If you start taking anti-cholesterol medication, you can reduce your risk by 30%.

What is your risk of heart attack in the next five years if you take the medication?

Answer: \_\_\_\_\_.%

6. Mammography is used to discover breast cancer in women. False positive tests are those tests that erroneously show a positive result. 85% positive mammographs are actually false positives. If 1000 women get mammography results, and 200 of them are informed that the results are abnormal, how many women are likely to actually have breast cancer?

Answer: \_\_\_\_\_ women

### Participant timeline

The participants from the School of Medicine will be tested at the first course at the beginning of the first academic year. The participants from the School of Humanities will be tested during their course on psychology in the same academic year. The testing is completed in a single day.

### Sample size

The sample size was calculated using the Sample Size Calculator (Medcalc, Ostend, Belgium).

We calculated the sample size based on the main outcome of the study: score on the knowledge/understanding test. We used the alpha of 0.05 and 80% power to detect the difference of average result in groups of people who correctly answered the questions. We used the data from the studies by Santesso et al. (2015) and Schwartz et al.(2009) to estimate that the difference of 40% in the knowledge score would be the size of effect relevant for our study. In those studies, 80% of the participants who received a summary of information in a table with event rates answered questions correctly compared with 20-40% of those who did not receive this information. We thus estimated that, at a minimum, 15 people in each group need to complete the survey so it can be compared between with the other group.

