### Objectives

The objective of our study is to evaluate the efficacy of infographics in presenting information, in terms of understanding and remembering research results, compared to standard PLS formats and scientific summary format.

The null hypothesis is that the proportion of the correct answers in all three groups is not going to differ significantly. The equation for that hypothesis is:

$$H_0: \text{Infographic} = \text{PLS} = \text{SciSumm}$$

The alternative hypothesis is that participants in the infographic group (Infographics) will have significantly more correctly answered questions about the topic than those in PLS group (PLS), meaning that infographics enables a better understanding of scientific findings than PLS. Also, the scientific summary group will have the lowest knowledge score of the three groups, meaning that scientific summary is not the suitable way of data presentation about a Cochrane review for lay population. The equation for that hypothesis is:

$$H_a: \text{Infographic} > \text{PLS} > \text{SciSumm}$$

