#### Claiming of the non-inferiority

For the primary outcome, non-inferiority of the experiment format to the control formats will be claimed if the lower limit of the CI (for the difference in average results between intervention group and control groups) is higher than the non-inferiority margin of 20%. The tests of superiority will be applied to the secondary outcomes. We want to perform the non-inferiority testing in order to prove that infographic is no worse than PLS and scientific summaries for information translation in terms of understanding of information. Also, the superiority tests will show that the infographic is better in terms of user satisfaction and accessibility of information compared to standard PLS and scientific summaries.

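### Fifteen per group does not give 80% power for the stated 40% difference read as the quoted proportions, and no power is stated for the non-inferiority claim

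*Combined protocol and SAP*

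**What the plan says.** The protocol's Sample size section bases the calculation on the knowledge score, with alpha 0.05 and "80% power to detect the difference of average result in groups of people who correctly answered the questions". From two earlier studies the authors "estimate that the difference of 40% in the knowledge score would be the size of effect relevant for our study". The support is given as proportions: 80% answered correctly with a table of event rates, "compared with 20-40% of those who did not receive this information". The conclusion is that "at a minimum, 15 people in each group need to complete the survey". The section gives no SD, sidedness, test or single comparison rate.

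Outcomes b) defines the primary outcome as a score out of 10. Table 1, under Inferential statistics, plans a three-group ANOVA or Kruskal-Wallis test for it.

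The hypotheses are stated in two ways. Objectives has a directional superiority alternative: the infographic group "will have significantly more correctly answered questions about the topic than those in PLS group". Claiming of the non-inferiority sets another criterion for the primary endpoint: "non-inferiority of the experiment format to the control formats will be claimed if the lower limit of the CI". The limit concerned is that of the between-group contrast in mean score, and the condition is that it "is higher than the non-inferiority margin of 20" per cent. The section then adds: "The tests of superiority will be applied to the secondary outcomes". That section gives no CI level.

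**The concern.** The stated effect, power and sample size should agree. When the 40% is read on the scale of the supporting rates, they do not: 15 per group gives less than the stated 80%. When it is read on the analysed score, a needed input is absent.

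The sizing also addresses detection of a difference, whereas the claim planned for the primary outcome is non-inferiority with a margin that the sizing never uses. If that claim fails, the stated 80% cannot help a reader judge whether the format or the number of participants is the reason. The confidence interval itself remains interpretable.

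**Working it through.** **Inputs from the Sample size section:** alpha 0.05; power 80%; difference 40%; rates 80% vs 20-40%; 15 per group. Sidedness is not stated. Both versions are shown because the alternative in Objectives is directional.

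**1. Which inputs give 15?** For two proportions, with p̄ the mean of p₁ and p₂:

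- pooled: n = [z_α√(2p̄(1−p̄)) + z_β√(p₁(1−p₁)+p₂(1−p₂))]² / (p₁−p₂)²
- unpooled: n = (z_α+z_β)² [p₁(1−p₁)+p₂(1−p₂)] / (p₁−p₂)²

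With 80% vs 30%, two-sided pooled: (1.960×√0.495 + 0.842×√0.37)² / 0.25 = 14.30, which rounds up to 15. Power at 15 is 82%. The difference is 50 points.

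**2. The stated 40 points.** Within 80% vs 20-40%, the only pair 40 points apart is 80% vs 40%. Two-sided pooled: (1.960×√0.48 + 0.842×√0.40)² / 0.16 = 22.33. Two-sided unpooled: (1.960+0.842)² × 0.40/0.16 = 19.62. One-sided versions use 1.645 in place of 1.960.

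| 80% vs 40%, no continuity correction | n | Rounded up | Power at 15 |
|---|---|---|---|
| Two-sided pooled | 22.33 | 23 | 62% |
| Two-sided unpooled | 19.62 | 20 | 69% |
| One-sided pooled | 17.47 | 18 | 74% |
| One-sided unpooled | 15.46 | 16 | 79% |

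Continuity correction raises the four values of n to between 20.2 and 27.1.

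**3. The 0-10 score.** Take 40% as 4 points and a two-sided pairwise t-test. At 15 per group the difference detectable with 80% power is 1.060 SD; at 14 it is 1.100 SD. So 15 is the required size only if the SD lies between 4/1.100 = 3.64 and 4/1.060 = 3.77. No SD is given. With assumed SDs of 2, 2.5, 3 and 3.5, power at 15 is over 99%, 99%, 94% and 86%.

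**4. Non-inferiority at 15 per group.** Assume that the margin means 2 points, so that the lower limit must lie above −2. With true difference δ in favour of the infographic, power is the probability that a noncentral t on 28 df, with noncentrality [(δ+2)/SD]√(15/2), exceeds the critical value. That value is 2.048 for a two-sided 95% CI and 1.701 for a one-sided 95% limit. For example, SD 2 and δ = 0 give noncentrality 2.739 and power 75%.

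| Per comparison | SD 2 | SD 2.5 | SD 3 |
|---|---|---|---|
| Two-sided 95% CI, δ = 0 | 75% | 56% | 42% |
| Two-sided 95% CI, δ = 1 point | 98% | 89% | 75% |
| One-sided 95% limit, δ = 0 | 85% | 69% | 55% |

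The SDs, δ, the CI level and the 2-point reading are all assumptions; the documents give none of them.

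**The case against.** The strongest reply is that 15 can be traced. Thirty per cent is the midpoint of the quoted 20-40%, and 80% vs 30% gives 15 with a two-sided pooled test, or 14.88 with a one-sided continuity-corrected one. One-sided unpooled 80% vs 40% gives 15.46, where 15 per group falls short of 80% by about one percentage point. This stands to the extent that a reader should not infer that 15 has no possible source. It does not rescue the stated effect: 80% vs 30% is a 50-point difference, the protocol nowhere names 30%, and 15.46 becomes 15 only by rounding down.

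A second reply is that the analysed outcome is a mean score, on which 15 per group is ample for a 4-point difference at SDs of 2 to 3. That is correct. A reader might infer that the trial is underpowered for its superiority comparison on the score. The documents do not support this, because on that scale the SD is simply missing.

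A third reply concerns non-inferiority. The protocol expects the infographic to do better, and a true advantage raises the power: at 2 points it is over 99%, 99% and 94% at SD 2, 2.5 and 3 (two-sided 95% CI). A reader might take the zero-difference row to show that the claim is underpowered, or set it against power for a 4-point superiority effect. Neither inference is supported. The documents do not assume a zero difference, and the second comparison uses a different truth for each claim. What stands is the omission: no section gives the power.

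**Conclusion.** The point holds in limited form and is worth correcting.

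- **Proportions.** Fifteen per group does not give the stated 80% power for the stated 40% difference. Power for 80% vs 40% is 62-69% two-sided and 74-79% one-sided without continuity correction, and 20-23 or 16-18 per group would be needed. This rests on reading the 40% as percentage points between the quoted rates. That 80% vs 30% was the pair actually used is an inference.
- **Score.** The figure cannot be verified. This is a missing input, not a contradiction.
- **Non-inferiority.** The sizing does not use the 20% margin, and no power is stated for the primary claim. That omission needs no assumption. Its size does: depending on SD, true difference and CI level, the cases tabulated run from 42% to 98% per comparison. Power to meet the margin against both control formats would be lower than for one comparison alone.

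**What to change.** Leave enrolment as it is and restate the effect or the power so that they agree with 15 per group.

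- **If proportions are kept:** either state the difference as 50 points (80% vs 30%, two-sided pooled, about 82% power), or keep 40 points (80% vs 40%) and state about 62% power (two-sided pooled). Name the sidedness and the formula.
- **If the score is used:** state, for example, that 15 completers per group give 80% power for a difference of 1.06 SD per unadjusted two-sided pairwise t-test at 0.05. Give the assumed SD; at SD 2, 2.5 or 3 this is 2.12, 2.65 or 3.18 points. Note that Table 1 plans a three-group ANOVA or Kruskal-Wallis test, which this pairwise figure does not describe.
- **For the non-inferiority claim:** confirm whether 20% means 2 points. State the power with its assumed SD, true difference and CI level, preferably over a range as in the second table above.

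The cost is wording only, plus a stated effect or power less favourable than the present one.

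### The 80% power with 15 per group is for one pairwise 40-point difference; it is not the power to confirm the hypothesised order Infographic > PLS > SciSumm

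*Combined protocol and SAP*

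**What the plan says.** The Objectives section gives one alternative hypothesis, Infographic > PLS > SciSumm. In words, the infographic group is to score significantly higher than the PLS group, and "the scientific summary group will have the lowest knowledge score of the three groups".

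The Sample size section describes a single contrast. It states "We used the alpha of 0.05 and 80% power to detect the difference of average result in groups" and settles on one effect: "the difference of 40% in the knowledge score would be the size of effect relevant for our study". The support comes from earlier studies, with a figure of 80% correct among readers given a table of event rates; the comparator figure was lower, "compared with 20-40% of those who did not receive this information". The conclusion is that "at a minimum, 15 people in each group need to complete the survey so it can be compared between with the other group".

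The section gives no SD for the knowledge score, no expected PLS score, no sidedness and no allowance for more than one comparison. Table 1, under Inferential statistics, lists Kruskal-Wallis or ANOVA for understanding, with no pairwise or ordered test. The section on claiming non-inferiority attaches a different claim to the same primary outcome, with a 20% margin.

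**The concern.** One effect, one alpha, one power and a singular other group describe a two-group calculation. The hypothesis has two adjacent steps, infographic over PLS and PLS over scientific summary, and neither has its own effect size or power.

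A reader who sees a single 80% will attach it to the stated hypothesis, and above all to infographic versus PLS, the first comparison named. If that comparison then turns out non-significant, the result may be read as showing no difference when the trial may have had little chance of showing one.

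**Working it through.** **Inputs from the plan.** Alpha 0.05, power 80%, difference 40 points, 15 completers per group, source rates 80% and 20-40% (all Sample size section); ordered alternative (Objectives).

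**Assumptions added here.** Two-sided tests, equal groups, a common SD, and the order counted as confirmed when both adjacent t-tests are significant in the stated direction.

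**1. The plan's figure of 15.** For two proportions (pooled variance, no continuity correction), n = [1.96·√(2p̄(1−p̄)) + 0.842·√(p1(1−p1) + p2(1−p2))]² / (p1−p2)².

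- 80% v 20%: 10 per group
- 80% v 30%: 15 per group
- 80% v 40%: (1.358 + 0.532)² / 0.16 = 22.3, so 23 per group

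The match at 15 is for a 50-point gap. At 15 per group, 80% v 40% as proportions has 62% power. For a difference in means the figure cannot be checked, because no SD is given. The basis of 15 is thus not established. The next steps take it at its word.

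**2. SD implied by 15 per group, 80% power and 40 points.** The t-test has 28 degrees of freedom and noncentrality d·√(n/2) = d·√7.5. Solving for 80% power gives d = 1.06, so SD = 40 / 1.06 = 37.7 points.

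**3. Power per step.** At SD 37.7, a 20-point step has d = 0.53 and 29% power; a 30-point step has d = 0.795 and 56%.

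**4. Power for both steps.** The two comparisons share the PLS arm, so their estimates have correlation −0.5, and joint power is below the product of the two powers. With 40 points on each step the product is 0.80 × 0.80 = 64%; simulation (200,000 trials) gives 61%.

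**5. What the source rates allow.** If 80% and 20-40% mark the best and worst arms (assumption), the span is 80 − 40 = 40 to 80 − 20 = 60 points. Two 40-point steps need 80, so at least one step falls below 40 points wherever PLS sits.

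| Arms (infographic / PLS / scientific summary) | SD | Infographic v PLS | PLS v scientific summary | Both |
|---|---|---|---|---|
| 40 points on each step | 37.7 | 80% | 80% | 61% |
| 80/50/20 | 37.7 | 56% | 56% | 24% |
| 80/40/20 | 37.7 | 80% | 29% | 18% |
| 80/60/40 | 37.7 | 29% | 29% | 4% |
| 80/50/20 | 30 | 75% | 75% | 53% |
| 80/60/40 | 30 | 42% | 42% | 11% |
| 80/50/20 | 25 | 89% | 89% | 78% |
| 80/60/40 | 25 | 56% | 56% | 25% |
| 80/50/20 | 20 | 98% | 98% | 95% |
| 80/60/40 | 20 | 75% | 75% | 53% |

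Moving PLS through the 60-point span at SD 37.7, joint power peaks at the midpoint, so about 24% is the ceiling under that assumption. Treated as proportions at 15 per group, joint power is about 10% (80/50/20) or 1% (80/60/40).

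**6. The listed omnibus test.** For ANOVA at SD 37.7, the noncentrality is 15·Σ(mean − grand mean)² / SD². That is 15 × 800 / 37.7² = 8.4 for 80/60/40 (71% power) and 15 × 1800 / 37.7² = 19.0 for 80/50/20 (97% power).

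**The case against.** The strongest reply is that the plan never says the 80% is for the order. Its wording is pairwise, it calls 15 a minimum, and the analysis it lists for understanding is an omnibus test with about 71-97% power at SD 37.7. The requirement of two significant adjacent tests is mine. That stands, and the joint figures must be labelled accordingly. But a significant omnibus result does not show infographic above PLS, and the plan gives no other power for its only alternative hypothesis.

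The SD is also open to challenge. A value of 37.7 is close to the largest possible for a 0-100 score with means of 80 and 40 (√((1600 + 2400)/2) = 44.7), which is doubtful for a ten-item sum. A smaller SD raises power a good deal, as the table shows. It does not rescue the stated calculation, though: at SD 20, 15 per group would give nearly 100% for 40 points, so 15 would not be the number that yields 80%.

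Two stronger readings are tempting, and the documents support neither.

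- A reader might infer that, on the plan's own figures, each adjacent step has 29-56% power and the order 4-24%. The plan gives no SD and no PLS position, and it does not map the source studies' rates onto its best and worst arms.
- A reader might infer that the 80% can belong only to infographic versus scientific summary. Under 80/40/20, infographic versus PLS differs by 40 points and has the full 80%. Under 80/50/20, the extreme pair differs by 60 points and has about 99%.

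The competing non-inferiority claim also stands as an objection: a final power statement needs one primary test to be fixed. That is a reason to say what the 80% covers, not to leave it open.

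**Conclusion.** The point holds in this form: the 80% is the power for one pairwise 40-point difference, whichever pair that is, and not for the three-arm order. Taking 15 per group and 80% as stated, and requiring both adjacent tests to be significant, joint power is about 61% even in the generous case of 40 points on each step. If the cited rates bound the arms, it is at most about 24%, and about 4% at 80/60/40.

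The size is uncertain because the plan leaves the inputs open. Over 80/60/40 and 80/50/20, with SDs from 37.7 down to 20, joint power runs from about 4% to 95%. The firm conclusion is that the stated power does not describe the stated hypothesis; the percentages show how large the gap could be.

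**What to change.** In the Sample size section:

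- State that the 80% applies to any single pairwise difference of 40 points and not to the order of the three arms.
- Give the power for infographic versus PLS, for PLS versus scientific summary, and for both together, over a stated range of SDs and step sizes, labelled as assumptions.

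In the analysis section, report both adjacent differences with confidence intervals, so that a non-significant infographic-versus-PLS result is not read as no difference.

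The revision should not assign the 40-point difference to infographic versus scientific summary, and it need not impose a new testing order.

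The cost is a change of wording and a less favourable power statement. No extra participants are needed.
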